8.4. DATA SOURCES

The data for this study will be collected from existing registries that include haemophilia patients living in the European region and in other countries. A feasibility assessment was performed between April 2023 and October 2023, designed against the EMA guidelines and requirements for registry-based studies (European Medicines Agency, 2021), to inform the selection of the registries for further engagement with the following objectives:

- Provide a general overview of HA disease registries in countries of interest, including details of their objectives, number of contributing sites, and funding sources.
- Assess the potential patient counts of moderate HA patients enrolled in each registry.
- Assess the availability, quality, completeness, frequency, and timeliness of variables required to meet the study requirements.
- Establish operational aspects of data management, including processes for data capture and validation.
- Describe current methods for identification and reporting on AEs, including adverse drug reactions and whether the relatedness to the treatment is reported.
- Identify any potential limitations, confounding factors and biases in the registries, as well as measures taken for mitigation.
- Outline any considerations relating to ethics, data privacy, informed consents, information governance and contracting.

Hemlibra—F. Hoffmann-La Roche Ltd Protocol BO44691, Version 2.0

Description of each of the registers was developed based on information collected from data holders and through desktop research. The full list of registries assessed can be found in Appendix 1. After the feasibility assessment the following registries were considered (listed in Table 7), these registries include a total of 5307 moderate HA patients. Participation of each data source is conditional to contracting.

Data source name	Data Collecti on Period	HA Patient Count	Moderate HA Patient Count	Longitudinal Follow-up	Data lag	Access to Patient- Level Data
UKNHD	1968 – Present	8959	836	YES	Up to 3 months	YES
FranceCoag	2003 – Present	7600	940	YES	Not specified	YES
HemoNED	2015- Present	1431	230	YES	2-3 weeks	YES
ATHNdataset	2020 - Present	100	15	YES	2-6 months	YES
WBDR	2018 – Present	10071	2987	YES	6 months	NO
CBDR	2015 – Present	2799	299	YES	Immediately available	NO

Table 7. Overview of the considered registries.

HA, Haemophilia A; **UKNHD**, UK National haemophilia database; **ATHNdataset**, American Thrombosis and Hemostasis Network; **WBDR**, World Bleeding Disorders Registry; **CBDR**, Canadian Bleeding Disorders Registry.

UK National Haemophilia Database (UKNHD)

The UKHCDO manages the UKNHD, which was established in 1968. All UK haemophilia centres are required to report to NHD on all patients with bleeding disorders. (UKCHDO, 2023). As of June 2023, 8959 patients diagnosed with HA were included in the database, and of those, 836 have moderate HA. Besides patient numbers and diagnosis, the database includes details of the type and quantity of treatment used for therapy and the complications of treatment (as described in section 8.3.1.). More recently, the Haemtrack application has allowed patients to report, via mobile apps or computers, their individual treatments, the reasons for those treatments (which includes, among other information, new bleeds, follow-up bleeds and prescribed treatments) and more details about the bleed episodes. The information uploaded by patients can be checked by their own haemophilia centre and treatment can be adjusted according to this information (UK National Haemophilia Database, 2020).

FranceCoag Registry / Reseau FranceCoag

The FranceCoag Network was established in 1994 to capture data on a cohort of French patients suffering from inherited deficiencies of coagulation proteins including HA disorder, at first the registry only included severe patients this was expanded in 2003 to include all patients with inherited bleeding disorders. The Network is a public institution hosted by both the Direction Recherche Santé (DRS) and Assistance Publique Hôpitaux de Marseille (AP-HM) and aims at improving epidemiological knowledge about inherited bleeding disorders in France. Patient data are collected after each follow-up visit from contributing sites via an electronic Case Report Form (CRF) and validated at least twice a year. This includes variables on demographics, treatment, medications, disease severity and diagnosis. The Network also captures both AEs and SAEs including international classification of diseases, tenth revision (ICD-10) only for malignant diseases (Doncarli et al., 2019). As of June 2023, the Network reported capturing data on more than 7000 HA patients including approximately 900 moderate HA patients.

HemoNED

HemoNED collects longitudinal data on patients with haemophilia and associated disorders in the Netherlands and is managed by the HemoNED Foundation, an initiative of the Dutch Haemophilia Treaters Society (NVHB) and the Netherlands Haemophilia Patient Society (NVHP). It was established in 2015. Practitioners treating haemophilia patients are able to enter data of their patients into the registry. Patients can also directly contribute to the registry by providing their medications and bleedings status in a digital infusion log (app), which is accessible to both the practitioner and the patient. The registry reports side effects of medication to both the Netherlands Pharmacovigilance centre and the EUHASS database (HemoNED). As of June 2023, the registry captured data on more than 1400 HA patients out of which 230 had moderate disease. Among others, data on diagnosis, disease severity, treatments, medications, demographics and bleeding events are periodically collected in the registry.

American Thrombosis and Hemostasis Network (ATHN)

The ATHN is a natural history cohort collecting data from patients with congenital or acquired non-neoplastic haematologic disorders. Data collection started on 2020 and includes information on demographics, clinical patient characteristics, treatments, medications, disease severity, diagnosis, inhibitor status among others. The data arecollected via an electronic CRF both from patients in the US and Pakistan. AEs are collected using SNOMED, and MedDRA standards including capture of TMA and TE events (American Thrombosis & Hemostasis Network, 2023). As of June 2023, a total of 100 patients with HA were reported including 15 patients with moderate HA.

World Bleeding Disorders Registry (WBDR)

The WBDR is a web-based data entry system established in January 2018 by the World Federation of Hemophilia (WFH). It aims to provide a platform for a network of treatment

Hemlibra—F. Hoffmann-La Roche Ltd Protocol BO44691, Version 2.0

centres to collect uniform and standardised data on people with HA or B, or von Willebrand Disease. As of February 2022, 96 participating centres from 46 countries had access to the WBDR (World Bleeding Disorders Registry, 2020). As of June 2023, a total of 10071 HA patients were estimated in the database, including 2987 with moderate HA. Data collection occurs at the level of participating treatment centres and includes a minimal data set that provides basic information on demographics, diagnostics, inhibitor status, bleeding events, joint disease, treatment, hospitalisation and mortality; as well as an extended data set that provides expanded details on the variables covered in the minimal dataset (Barbara Konkle et al., 2020).

Canadian Bleeding Disorders Registry (CBDR)

The CBDR, launched in July 2015, is a clinical database that collects information on virtually all patients affected by bleeding disorders in Canada, using a standardised dataset, data quality control processes, and incentivising mechanisms for Canadian Hemophilia Treatment Centres. As of June 2023, a total of 2799 HA patients were in the database, which included 299 patients with moderate HA. CHESS is a haemophilia surveillance system that was introduced in 2015, capturing data related to treatment safety and efficacy, plasma clotting factor utilisation and HRQoL data; and is compatible with the other data collection resources operating in Canada (Canadian Health Registry/ Canadian Hemophilia Assessment and Resource Management information System). The CBDR database is owned by the Association of Hemophilia Clinic Directors of Canada, and McMaster University is the data custodian. Patient demographics, clinical data, treatment usage and outcome data are collected via two main mechanisms: patients can enter information about their treatment and the bleeding events into the myCBDR app; and clinicians and others involved in the care of the patient can add specific data as part of documenting clinical interactions with the patient (lorio et al., 2022).

8.5. STUDY SIZE

The study aims to include all available patients exposed to emicizumab with moderate congenital HA without FVIII inhibitors and with severe bleeding phenotype. In section 8.5.1. a real-world estimate is presented of expected number of eligible patients who can be included within the study period, based on a feasibility assessment. To assess whether this expected number of eligible patients will be adequate to investigate the primary study objective of determining the crude incidence rate (IR) of 1st TE, a simulation based statistical estimation is presented in section 8.5.2.

8.5.1. Expected emicizumab uptake in the patient population

Using information from the feasibility assessment conducted between April and October 2023 and the assumptions listed below, 2 scenarios of expected number of emicizumab patients during the cohort entry period (MA- 2026) were made. One scenario including

all available data sources and one restricted to data within the EU as the extension of indication for emicizumab to include prophylaxis in patients with HA without FVIII inhibitors, moderate disease severity and severe bleeding phenotype occurred recently in the EU (23 January 2023).

- **Assumption 1:** Inhibitor prevalence of 10% for moderate HA patients (Witmer and Young, 2013).
- Assumption 2: Severe bleeding phenotype prevalence of 30% among moderate HA patients without inhibitors based on requiring some form of prophylaxis (den Uijl et al., 2014).
- Assumption 3: Registry-based numbers of moderate HA patients treated with emicizumab roughly correspond to those with inhibitors (*patients without inhibitors are expected to be captured at least 12 months after the label extension approval due to later reimbursement approvals and data lag in the registries*). In addition, due to the feasibility assessment including patients from registries based in the US and Canada and the earlier approval of an extension of indication among moderate HA patients without inhibitors in these countries, the validity of assumption 3 could be affected. To reduce the impact of this, a more conservative scenario where the calculation was only based on feasibility information originating from countries within the EU was also calculated. Finally, MA most often comes before reimbursement approval, however, this is true for both periods and it is assumed that it will not impact the overall estimation.
- Assumption 4: Moderate HA patient population without inhibitors uptake during the cohort entry period (MA [2023 in the EU] 2026) is expected to be equal to moderate patient HA population with inhibitor uptake (MA [2018 in the EU] feasibility assessment).

To derive the uptake percentage of emicizumab, the above assumptions were utilised in the data from the feasibility assessment as below to produce the following uptake scenarios. Scenario 1 included all available data sources and scenario 2 was restricted to data within the EU.

- 1. The feasibility assessment reported 54 patients treated with emicizumab among 1319 patients with moderate HA, 4 registries (ATHNdataset, CBDR, FranceCoag and CNHPR) provided data on the number of emicizumab users in their moderate patient population. Given that ~10% of the moderate HA patient population have inhibitors (assumption 1), ~132 patients out of the 1319 patients would be eligible for treatment with emicizumab, as the approved indication for emicizumab was only for moderate HA patients with inhibitors when these data were collected (assumption 3). This indicates that the uptake percentage is approximately 40% (54/132). The above calculation of 40% is also in line with internal Roche data on uptake among moderate HA patients with inhibitors of ~45% and only slightly lower than an earlier projected uptake of emicizumab for 2023 in severe patients without inhibitors (Stonebraker and Ducore, 2021).
- 2. In the second scenario only patients from data sources within the EU (FranceCoag and Czech National Haemophilia Programme [this registry is not

Hemlibra—F. Hoffmann-La Roche Ltd Protocol BO44691, Version

2.0

40

considered for inclusion in the study but contributed information on the number of moderate patients currently treated with emicizumab]) were included, increasing the validity of assumption 3, as treatment with emicizumab among moderate patients without inhibitors was approved in 2023. The feasibility assessment found 1005 moderate patients out of which 26 were treated with emicizumab. Applying the same assumptions as was made in the example above an expected uptake of 25% was derived.

Using the uptake percentages presented above, projections of the expected study size for patients in the extended indication until 2026 are provided. It is assumed that the uptake in patients without inhibitors will be similar to that of moderate patients with inhibitors (assumption 4). In addition, based on assumption 1, the study cohort consists of 90% of moderate HA patients without inhibitors. Out of those, 30 % will have a severe bleeding phenotype (assumption 2). Four study size scenarios are presented in Table 8.

 Table 8. Emicizumab uptake among moderate HA patients without inhibitors and severe bleeding phenotype.

Scenarios explored	Total study population of moderate HA patients in registries	Expected HA patients without inhibitors (90%)	Expected moderate HA patients with severe bleeding phenotype (30%)	Uptake % of emicizumab	Expected moderate HA patients initiating emicizumab
Using all data	5000*	4500	1350	40%	540
sources for uptake %*	3000	2700	810	40%	324
Using EU only data	5000*	4500	1350	25%	338
sources for uptake %*	3000	2700	810	25%	202

*Approximate total expected moderate patient population in all considered registries. **HA**, Haemophilia A; **EU**, European Union.

For the study cohort, using a conservative estimate with a total study population of 3000 moderate HA patients (as indicated in Table 8), we project ~202 patients newly exposed to emicizumab to be captured within the cohort entry period (MA- 2026).

8.5.2. Minimum required sample size

To assess whether the real-world estimate obtained in section 8.5.1. will be adequate to investigate the primary study objective of determining the crude IR of 1st TE, a statistical estimation is presented below. A target sample size of ~200 exposed patients with an average follow-up of 4 years for each patient was considered. From simulation runs, this target sample size will ensure 88% probability that the 95% Clopper-Pearson confidence

interval (CI) of the crude IR does not exceed a threshold value of one event per 100 person-years (PY), considering the expected IR of AEs for the primary objective of 0.15 events per 100 PY.

In the emicizumab clinical trial program, a 0.38% incidence risk (3 out of 798 patients) was observed and an IR of 0.15 events per 100 PY with a 95% CI (0.03-0.44) for serious TE events not associated with concomitant aPCC in HA patients. The average duration of exposure was 138 weeks (2.65 years), with a median duration of exposure of 104 weeks (2 years). These findings align with the TE event risk observed in the European Haemophilia Safety Surveillance (EUHASS) registry, which was 0.40% (4 out of 1319 patients).

Table 9 presents alternative scenarios for the estimation's accuracy, defined as the probability that the upper limit of the IR 95% CI does not exceed a certain threshold. This is obtained via calculations with different target sample sizes. For the first alternative scenario, the same expected event rate as above is assumed, and the threshold value for the 95% CI remains as indicated previously. In the second scenario the expected event rate is increased to 0.5 per 100 PY and the threshold value for the 95% CI is changed to 1.5 events per 100 PY.

	Accuracy CI								
Target Sample Size	Expected event rate: 0.15 per 100 PY Threshold: 1 event per 100 PY	Expected event rate: 0.5 per 100 PY Threshold: 1.5 event per 100 PY							
N=175	72%	73%							
N=200	88%	79%							
N=225	95%	83%							

Table 9. Accuracy estimation for different targets of sample sizes, expected event rates and Clopper-Pearson 95% CI threshold values.

CI, Confidence Interval; N, Sample Size; PY, Person Years.

8.6. DATA MANAGEMENT

IQVIA is anticipated to perform the data management and statistical analyses. IQVIA will conduct this PASS on behalf of the MAH and will be responsible for applying for the applicable study permits, obtaining necessary approvals (ethical or otherwise), and accessing the study data. The data will be stored and analysed in accordance with local policy based on the country in which each registry is based. The primary data holders collect and manage data according to their own standards.

Hemlibra—F. Hoffmann-La Roche Ltd Protocol BO44691, Version 2.0

It is anticipated that the data holders will make data accessible to IQVIA, according to data permits in each specific country. The details of the data permits will be confirmed only once the data permits are granted. If the data permits allow patient-level data (PLD) will be accessed by IQVIA, otherwise only aggregate data will be transferred to IQVIA. All PLD accessible to IQVIA will have original personal identifiers replaced with a study identification number. Thus, IQVIA will not have access to data that allow patients to be directly identified. Following the extraction from the data sources, anonymised data will be stored at secure IQVIA servers or at other secure location in accordance with requirements of the data sources. Access to the data will be restricted to relevant personnel. It is not anticipated for the MAH to have access to the PLD. If the IQVIA is not granted access to PLD aggregated will be accessed by IQVIA using a CDM, as described in more detail below.

IQVIA will adhere to all local and regional laws on data protection and privacy set forth by each of the study countries. IQVIA will also adhere to IQVIA standard operating procedures (SOPs); data management for this study will be conducted using standard IQVIA processes. IQVIA will maintain appropriate data storage, including periodic backup of files and archiving procedures and will comply with procedures that include checking electronic files, maintaining security and data confidentiality, following analyses plans and performing quality checks for all programmes.

The general principles of data management and statistical analyses will be described in detail in the Data Management Plan (DMP) and SAP, respectively. Routine procedures will include checking electronic files, maintaining security and data confidentiality, following analysis plans, and performing quality control (QC) checks of all programmes. All data checks to be performed on completeness, plausibility, and consistency of collected data will be described in detail with identification of data discrepancies.

Data will be harmonised and standardised as appropriate using a CDM. Within each data source, a CDM will be used to create aggregated datasets from the collected PLD in a pre-defined standard format. This CDM defines appropriate level of aggregation and minimum information required to enable the statistical analysis of the study objectives.

For registries with only aggregated data transfer and no access to PLD by IQVIA, the CDM will be applied by the data provider to create the aggregated data from the specific data source based on data specifications provided by IQVIA. These aggregated datasets are then delivered to IQVIA who then will perform the centralised data collection and statistical analysis of the study. In such cases, only aggregated data will be transferred to IQVIA servers.

For an overview of the data sources that allow for access to PLD, please refer to Table 7.

Hemlibra—F. Hoffmann-La Roche Ltd Protocol BO44691, Version 2.0

Once at the IQVIA servers, the aggregated data originating from the data sources will be combined with the aggregated PLD analysed by IQVIA.

A brief overview of the proposed CDM workflow depicting the different stages as described above is shown in Figure 2. The workflow presented constitutes a high-level overview of the CDM process and exact details especially how this would translate to the underlying programming pipeline and output generation will be detailed in DMP and SAP.

Figure 2. A high-level overview of CDM workflow.

IQVIA will develop a DMP for the purpose of this study. DMP will be created before data collection begins and will describe in detail all data checks to be performed on completeness, plausibility, and consistency for collected data and all steps necessary from raw data to final database such as, but not limited to, database development, additional data collection process, medical coding considerations and conventions, query edition and database validation.

Hemlibra—F. Hoffmann-La Roche Ltd Protocol BO44691, Version 2.0

8.7. DATA ANALYSIS

8.7.1. General Considerations

This study does not include any formal comparison and is purely descriptive. The following sections describe the analyses that will be carried out. Data analyses might be stratified as described in section 8.7.3. depending on data availability and final patient counts. In addition, no formal comparisons will be conducted between prophylaxis vs non-prophylaxis-treated patients (last previous treatment before the patient started emicizumab). Patient demographic and clinical characteristics will therefore be included in the descriptive analyses presented by patient subgroups. A full description of the analytical approach, data derivations, category definitions, analyses and presentation of the study results will be detailed in the SAP.

8.7.2. Planned Analyses

For the analysis of the primary objective and secondary objectives 1, 2, and 3 the overall crude and crude stratified IRs will be calculated. The person-time of each patient will be based on the follow-up and censoring criteria presented in section 8.2.4. and 8.2.5.

For the calculation of crude IRs, the denominator will be the pooled person-time of all the patients within the cohort. The patient time-at-risk will be calculated from index date until the date of an incident event or censoring, whichever occurs first. All first events occurring during follow-up period will be counted in the total number of events. Crude IRs will be presented per 100 PY with 95% CI.

For the primary objective, the numerator will be the number of first TE events of all patients within the cohort. For secondary objectives 1, 2, 3 the numerator will be the number of first occurrences of any SAE; TMA events or serious systemic hypersensitivity reactions, including anaphylaxis; respectively.

For the analysis of secondary objective 4, calculation of crude stratified IRs of 1st TE events will be done. The events will be counted for each category/stratum of relevant pre-defined risk factors (see section 8.3.2.4. for a listing of considered risk factors). More details on the risk factor based tabulations will be presented in SAP.

For analysis of secondary objective 5, characteristics of TE events, SAEs, TMA, and serious systemic hypersensitivity reactions, including anaphylaxis (e.g., diagnosis and symptoms), will be tabulated. In addition, time to 1st TE event; time to 1st TMA event; time to 1st serious systemic hypersensitivity reactions, including anaphylaxis; and time to any 1st SAE event will be described by Kaplan-Meier curves.

For analysis of secondary objective 6, calculation of crude IR and crude incidence proportion of TE, TMA events, SAEs and serious systemic hypersensitivity reactions, **Hemlibra—F. Hoffmann-La Roche Ltd** Protocol BO44691, Version 2.0

including anaphylaxis, will be calculated and tabulated for FVIII prophylaxis use (yes/no) prior to emicizumab treatment.

Patient demographic and clinical characteristics will also be tabulated in relation to the AEs (TE events, SAEs, TMA events and serious systemic hypersensitivity reactions, including anaphylaxis) and in total.

Continuous variables will be described using mean, standard deviation, median, first and third quartiles, interquartile range, minimum and maximum, as appropriate. Categorical variables will be described by means of counts and percentages (relative to the number of non-missing observations for each variable).

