8.3.1. Primary and Secondary Safety Variables

The primary safety variable is TE events as recorded in the data source.

The secondary safety variables are:

- TMA
- Serious systemic hypersensitivity reactions, including anaphylaxis
- SAEs (for definition of SAEs see section 10.1.2.)

The relationship to the treatment will be detailed according to available information in each registry. If this is not available in the registry, time to the first primary or secondary safety events will be described, for further details see section 8.7.

The reporting of AEs in the considered registers for further engagement differs, an overview is given in Table 3 and the details are provided below.

Table 3.	Reporting	of adverse	events among	the considered	data sources.
			U		

Data source	Country	Coding standard
UKNHD	UK	Local adaptation of EUHASS
FranceCoag	France	EUHASS (ICD-10 used for further classification of malignant disorders)
HemoNED	Netherlands	EUHASS
ATHNdataset	US	SNOMED, MedDRA
WBDR	Multi-country	Standardised module
CBDR	Canada	CHESS

UKNHD, UK National haemophilia database; **UK**, United Kingdom; **EUHASS**, European Haemophilia Safety Surveillance; **ATHNdataset**, American Thrombosis and Hemostasis Network; **US**; United States; SNOMED **CT**, Systemized Nomenclature of Medicine – Clinical Terms; **MedDRA**, Medical Dictionary For Regulatory Activities; **WBDR**, World Bleeding Disorders Registry; **CBDR**, Canadian Bleeding Disorders Registry; **CHESS**, Canadian Hemophilia Surveillance System; **ICD**, International Classification Of Diseases.

The European Haemophila Safety Surveillance (EUHASS) system is a pharmacovigilance program that aims to monitor the safety of treatments for patients with haemophilia and other inherited bleeding disorders in Europe through a prospective AE reporting system. The program started in October 2008 and includes participating centres located across more than 30 European countries. The following events are reported to EUHASS either as they occur or as a minimum at the end of every 3-month surveillance period (European Haemophilia Safety Surveillance, n.d.):

- Acute or allergic events
- Transfusion-transmitted infections
- Inhibitors
- Thromboses
- Malignancies
- New cardiovascular events
- Neurological events
- Unexpected Poor Efficacy
- Other AE Possibly Related to Concentrate
- Deaths

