For each event reported, data are collected on the patient's age, diagnosis and severity; as well as details about the product and batch numbers involved; and finally details about the event outcome and presence of other risk factors (Makris et al., 2011). Event-specific data are submitted anonymously using the Soundex coding system to avoid

Hemlibra—F. Hoffmann-La Roche Ltd

Protocol BO44691, Version 2.0

duplicate reporting. EUHASS data are not collected according to the medical dictionary for regulatory activities (MedDRA) classifications; however, AEs have been previously aligned to MedDRA preferred terms.

For the UKNHD data source, event reporting has been harmonised with the EUHASS program, and any reported event from participating centres are anonymised and automatically forwarded to EUHASS by the National Haemophilia Database (NHD). Yet, whenever a new inhibitor is reported, the UK Haemophilia Centre Doctors' Organisation (UKHCDO) requests more detailed information, which is not passed onto EUHASS. The additional data requested by the UKHCDO when a new inhibitor is reported include (World Federation of Hemophilia, 2009):

- Coagulation disorder, severity, and genotype if known
- Any relatives with inhibitors
- First inhibitor detection date and the reason for the test
- Inhibitor value at first detection and maximum value
- Any change in the value of factor VIII- or factor IX-coagulant (FVIII:C or FIX:C)
- Any change in bleeding pattern
- Treatment protocol before inhibitor development
- Time in chronological and exposure days from first dose to inhibitor development

The Canadian Hemophilia Surveillance System (CHESS) uses the same methodology as the EUHASS program (Dolan et al., 2014).

For the WBDR data source, an AE module is available at both baseline (when the patient enrolled in the registry) and follow-up visits. When an AE is reported, the participant centre must complete the following fields:

- Start date of onset (i.e., the date the patient first experiences the AE)
- Events (Infection, allergic reaction including anaphylaxis, TE event, TMA, lack of efficacy, injection site reaction or other event)
- Date of resolution (i.e., the date by when the patient stops experiencing the AE)
- Interventions

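### The TMA incidence rate is divided by person-time from all registries, although TMA capture is described for only two of the six, so the rate and its upper limit may be too low

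*Protocol*

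**What the plan says.** Section 8.7.2 covers the primary objective and secondary objectives 1 to 3 with one rule: "the denominator will be the pooled person-time of all the patients within the cohort". The numerators for the secondary objectives are the "number of first occurrences of any SAE; TMA events or serious systemic hypersensitivity reactions, including anaphylaxis; respectively". "Crude IRs will be presented per 100 PY with 95% CI". The synopsis repeats the pooled denominator. Neither place restricts it by registry or by outcome.

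Section 8.3.1 and its Table 3 describe how adverse events are recorded:

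- **UKNHD (local adaptation), FranceCoag and HemoNED** use EUHASS. The ten EUHASS headings listed include thromboses, acute or allergic events and deaths. TMA is not named. The residual heading is "Other AE Possibly Related to Concentrate".
- **CBDR** uses CHESS: "The Canadian Hemophilia Surveillance System (CHESS) uses the same methodology as the EUHASS program".
- **WBDR** has an adverse event module with a TMA item: "Events (Infection, allergic reaction including anaphylaxis, TE event, TMA, lack of efficacy, injection site reaction or other event".

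For **ATHNdataset**, Section 8.4 states: "AEs are collected using SNOMED, and MedDRA standards including capture of TMA and TE events".

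**The concern.** A crude rate is interpretable only if the person-time in its denominator is time during which the event would have been recorded. Where a registry's scheme does not ask for TMA, a patient-year there adds to the denominator but may be unable to add to the numerator. It is then counted as event-free. The error runs one way: the rate and its upper confidence limit both fall.

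For a rare event the likely result is zero or one case, and the upper limit is then the main finding. A zero-event TMA result would look more reassuring than the data allow.

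Nothing else in the protocol picks this up:

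- The sensitivity analyses of Section 8.7.4 vary censoring, repeat events, the follow-up cap and the bleeding phenotype, but not outcome ascertainment. The ENCePP checklist nevertheless cites that section for control of outcome misclassification (item 10.6).
- The regional subgroup in Section 8.7.3 puts the US and Canada together, and so mixes a source described as capturing TMA with one that is not.
- Section 8.9.2 says in general that validity depends on registry completeness, but the heterogeneity it goes on to discuss concerns exposure and lookback.
- Tables 1, 4, 5 and 6 grade the availability of phenotype, treatment and patient variables. Table 3, on adverse events, lists coding standards only.

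A related question arises for SAEs. Sections 10.1.1 and 10.1.2 define them by outcome, whatever the cause, while the EUHASS residual heading depends on a possible relation to concentrate. The protocol does not show how such lists yield SAEs as defined.

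**Working it through.** **Inputs**

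- Person-time: "A target sample size of ~200 exposed patients with an average follow-up of 4 years for each patient was considered" (Section 8.5.2), so 200 × 4 = 800 person-years (PY).
- Moderate haemophilia A counts (Table 7): UKNHD 836, FranceCoag 940, HemoNED 230, ATHNdataset 15, WBDR 2987, CBDR 299; total 5307.
- Exact two-sided 95% upper limit for x events: U(x) = χ²(0.975; 2x + 2) / 2, divided by PY.

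**Step 1: the plan's own figure**

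The upper limit on 800 PY is 0.90 per 100 PY for 2 events and 1.10 for 3, so at most 2 events keep it at or below 1. With a true rate of 0.15 per 100 PY the mean is 1.2, and P(X ≤ 2) = e^(−1.2) × (1 + 1.2 + 0.72) = 0.880. The stated 88% is reproduced, so 800 PY is the right basis.

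**Step 2: share of person-time with described TMA capture**

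Assumption: person-time is shared like the moderate patients of Table 7.

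- TMA named: 2987 + 15 = 3002; 3002 / 5307 = 0.566, or 0.566 × 800 ≈ 452 PY.
- TMA not named: 836 + 940 + 230 + 299 = 2305; 2305 / 5307 = 0.434.

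**Step 3: effect on the rate**

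If the true rate is the same everywhere and the four registries capture a fraction c of TMA cases, then pooled rate / true rate = 0.566 + 0.434c. At c = 0 this is 0.57, at c = 0.5 it is 0.78, and at c = 1 it is 1. Any c below 1 lowers the rate.

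**Step 4: effect on the upper limit (worst case, c = 0)**

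| TMA events | All 800 PY | About 452 PY |
|---|---|---|
| 0 | 3.689 / 800 = 0.46 | 3.689 / 452.5 = 0.82 |
| 1 | 0.70 | 1.23 |
| 2 | 0.90 | 1.60 |

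(upper 95% limit per 100 PY)

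**Step 5: other covered shares, zero events**

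The actual mix of emicizumab users is not known. With covered share s, the limit is 3.689 / (800s): 0.61 per 100 PY at 75%, 0.92 at 50% and 1.84 at 25%.

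**SAEs.** No calculation is possible, because the protocol does not say which registries, if any, fail to capture SAEs.

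**The case against.** **TMA may be recorded under another heading.** The protocol does not call the EUHASS list exhaustive. A case could be filed under the residual heading, thromboses or deaths. Section 8.3.1 says EUHASS events have been aligned to MedDRA preferred terms, which suggests detail below the headings. UKNHD uses a local adaptation whose content is not shown. Section 8.4 says that FranceCoag has its own electronic form and that HemoNED also reports side effects to a national pharmacovigilance centre. This stands. A reader might infer that TMA cannot be recorded in these four registries, but the documents show only that it is not named.

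**The 0.57 is not an estimate.** It needs zero capture in all four registries and a Table 7 mix of users. Section 8.5.1 has emicizumab counts from only four registries, and WBDR is not among them. This stands, and the figure is given here as a worst case. Likewise, TMA is unnamed in most registries by count (4 of 6) but not by patients (43%).

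**SAEs.** A reader might infer that most registries have no place for SAEs, so that the SAE rate is biased too. The documents do not support that. Appendix 1 made SAE/AE coverage a condition of selection, and Section 8.4 says that FranceCoag captures SAEs and that WBDR records hospitalisation and mortality. What remains is that the route from event lists to the definition in Section 10.1.2 is not shown.

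**This belongs in the SAP.** Mapping of events and operational definitions are indeed left to the SAP. But mapping can recode only what was recorded, and the denominator itself is fixed in the protocol. On this point the objection fails.

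**Restriction could discard real cases.** This is a fair warning, and the fix keeps the all-registry figure for that reason.

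**Conclusion.** The point holds for TMA. The protocol fixes a pooled denominator with no ascertainment condition, while its own registry descriptions support TMA capture in only two of six sources. The pooled TMA rate and its upper limit may therefore be too low. The extent lies between no bias (full capture in the other four) and the worst case: 43% of person-time uninformative, the rate at about 0.57 of that in covered person-time, and a zero-event limit of 0.46 instead of about 0.82 per 100 PY. These figures assume 800 PY and the Table 7 distribution.

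For SAEs the protocol leaves the derivation unclear, but does not show that capture is absent, and no size can be stated.

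A reader might also infer that the main result is compromised. It is not. Thromboses are a EUHASS heading, and WBDR and ATHNdataset are described as capturing thromboembolic events, so the primary rate and the 88% figure are unaffected.

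**What to change.** In Section 8.7.2, and in the matching synopsis text:

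1. Add a table that confirms with each registry whether TMA, and SAEs as defined in Section 10.1.2, are ascertained.
2. Calculate each outcome's rate and confidence interval with events and person-time only from registries confirmed to ascertain that outcome.
3. Report the all-registry rate beside it as a labelled supplementary figure, which retains any case recorded elsewhere.

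If the four registries confirm that they capture TMA, their person-time stays in and the result does not change.

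The cost is a wording change, one table and one query to each registry. The common data model already aggregates within each source, so restricting by registry should need little extra programming. The downside is fewer person-years and wider intervals for TMA, and possibly for SAEs.
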